Adherence, however, has been a major challenge in the treatment of Hepatitis C infection, especially before Sofosbuvir and Simprevir were introduced. Aside from side effects, Ribavirin has to be taken twice daily, while Interferon is injectable. Boceprevir and Telaprevir also had their fair share of side effects, drug interactions and multiple daily dosing which impaired treatment adherence. Studies on these medications have shown that the proportion of missed doses increases over time, and are associated with failure of treatment [11-14]. In one analysis of 2 clinical trials, patients who took their medications $\geq 80-85\%$ of the time achieved SVR 86-90% of the time, while those $< 80\%$ adherent attained SVR only 8-32% of the time [28]. Aside from HCV medication-related issues, these patients may have other co-morbidities such as psychiatric disorders which can negatively influence patient compliance [18]. The matter of polypharmacy in patients co-infected with HIV and HCV can also be a major concern in terms of adherence [19].

Treatment adherence studies for Hepatitis C were mostly small studies of patients taking Pegylated-Interferon and Ribavirin [11-14]. These reports showed higher treatment success for patients who were at least 80-90% compliant, with most failures reported in patients with compliance rate around 70-80%. However, most of these also relied on patient self-reporting, pill counting and pharmacy refill data, which are inherently imprecise.

With the enhanced tolerability, lower drug-drug interactions, side effect profile and once daily dosing of the new DAA's, adherence has improved but is still an area of concern. In registration clinical trials, those who relapsed on Sofosbuvir were patients who did not comply to their treatment regimen [15]. The same holds true for Simeprevir, and these patients also developed resistant HCV [16]. With the standard 12-weeks course of these medications costing in the range

of \$100,000 - \$140,000, patients needing repeat treatment after relapsing can be very expensive [10], making treatment compliance even more important. It would also be very costly for treatment-experienced patients to be re-treated because of failure due to compliance.

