Electronic assisted compliance is not the sole indicator of MEMS, it is also used in conjunction with answers about demographics, clinical state and symptoms to learn more about the patient characteristics that influence whether a medication regimen is adhered to.

Portal724-MEMS is HIPAA Complaint and ISO27001 Certified. The Electronic Data Capture, the Data Transfer and Data Access are all confidential and Secure in every stage of the Data

Flow Model. The device to be used in this study is a Smart Cap with Pill Dispensing and Integrated Cellular Modem.

Objective

Primary: To determine the effect of the use of Portal724-MEMS Service on medication adherence in the treatment of Hepatitis C patients with grazopravir/elbasvir with or without Ribavirin, defined as compliance to regimen 95% of the time.

Methods

Study design: Open-label, randomized, single center pilot study.

Treatment Arms:

Genotype 1a, treatment naïve or PegIFN/RBV experienced without baseline NS5A polymorphisms with elbasvir/grazoprevir for 12 weeks

Genotype 1a, treatment naïve or PegIFN/RBV experienced with baseline NS5A polymorphisms with elbasvir/grazoprevir/ribavirin for 16 weeks

Genotype 1b, treatment naïve or PegIFN/RBV experienced for 12 weeks

Genotype 1a or 1b, PegIFN/RBV/PI-experienced with elbasvir/grazoprevir/ribavirin for 16 weeks

Genotype 4: treatment naïve with elbasvir/grazoprevir for 12 weeks

Genotype 4: PegIFN/RBV- experienced with elbasvir/grazoprevir/ribavirin for 16 weeks

Proposed number of participants: 40 patients infected with HCV (20 for each group)

Data Collection Time Period: approximately 1 year

Site of Enrollment:

Liver Center at Saint Michael's Medical Center. [name].

In the Liver Center, the main Hepatitis / Infectious Diseases Physician that this study will collaborate with is [name], MD.

Study Patient Population

Treatment-naïve and treatment-experienced genotype 1 and 4 HCV patients with or without compensated cirrhosis will be enrolled in this study.

The inclusion criteria for study are as follows:

1. Male or female 18 years old and above.
2. Be HCV treatment naïve
3. HCV RNA PCR \geq 10,000 IU/L
4. Confirmed infection with Hepatitis C virus (HCV) by HCV serum antibody assay and by HCV Ribonucleic Acid (RNA) Polymerase Chain Reaction (PCR) and Confirmed chronicity with 2 PCR's 6 months apart.
5. Patients with HCV Genotype 1, 4

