- hormonal contraceptive: oral contraceptive pill (estrogen/progestin pill or progestinonly pill), contraceptive skin patch, vaginal contraceptive ring, or subcutaneous contraceptive injection

†Abstinence (relative to heterosexual activity) can be used as the sole method of contraception if it is consistently employed as the subject's preferred and usual lifestyle and if considered acceptable by local regulatory agencies and ERCs/IRBs. Periodic abstinence (e.g., calendar, ovulation, sympto-thermal, post-ovulation methods, etc.) and withdrawal are not acceptable methods of contraception.

0455LH

Enrollment

Upon signing the informed consent, the following data will be gathered prior to start of treatment: demographic data such as age, gender, race/ethnicity, highest educational attainment, employment status, co-morbid conditions as documented in the patient's records, current medications, vital signs (blood pressure, heart rate, respiratory rate, temperature), CBC with differential count, complete metabolic panel, 12-Lead Electrocardiogram (EKG), Cardiac stress test results if applicable, echocardiogram results if applicable, , BMI, baseline HCV RNA PCR

viral load, HCV genotype, baseline HCV resistance testing (if indicated), results of the Fibroscan® test or liver biopsy.

Once the informed consent is signed and the patient is deemed eligible for treatment, the patient will be randomized to either ARM 1 or ARM 2 in a 1:1 ratio. ARM 1 will be prescribed elbasvirir/grazoprevir with/or without ribavirin for 12 or 16 weeks 1 tablet daily with MEMS Smart Cap with real-time monitoring. Arm 2: elbasvir/grazoprevir with/or without ribavirin for 12 or 16 weeks 1 tablet daily MEMS Smart Cap without real-time monitoring.

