For Group 1, the cap of the study drug bottle will be replaced with the Portal724- MEMS Smart Cap. A cellular phone per patient will also be provided. The Smart Cap in this study is to be outfitted to send messages to a website to which only the investigators and the research assistants have access to monitor medication adherence. Patients are to be instructed to open their study drug bottles in areas where there is at least 1 cellular signal bar. Patients will also be instructed to take their medications at specific agreed upon times. Once the agreed upon times are set, these will be programmed into the Smart Caps through a software program. The Smart Caps are encoded to not only record each pill bottle opening, it also will transmit an alert to the aforementioned website when the bottle is not opened within 2 hours of the agreed upon time. This alert is then seen by the Investigator or the Research assistant through a computer or their smartphone. The Investigator or Research Assistant in turn calls the cellular phone provided to the patient to remind the participant to take their medication, thus providing real-time feedback. Group 2 (the control group) will be provided MEMS Smart Cap to record study drug bottle opening, but without real-time feedback and will be managed as per the standard of care at the Liver Center SMMC.

Patients from both groups will be seen in the Liver Center at Day 1, weeks 2, 4, 8 and 12 from start of treatment. They will be seen by Liver Center Physician together with the Investigator and Research Assistant at each visit. They will also be counseled about the importance of medication adherence at every visit by the Liver Center physician. At each visit, patients are instructed to bring with them all of their anti-HCV study drug bottles for pill counting to be done by the Investigator and Research Assistant. Patients in ARM 1 will also get feedback about their medication compliance using the Smart Caps per visit.

After completion of treatment as determined by the Liver Center Physician, patients from both groups are to follow-up at week 4 and week 12 post-treatment. At that time, an HCV RNA PCR viral load will be obtained to determine if patient has an undetectable viral load, or Sustained Virologic Response (SVR). SVR is the marker for a functional cure of HCV, or treatment success. Non-SVR would mean treatment failure.

Study Procedures	Pre-Treatment						Treatment Assessments		Post Tx	Post tx

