	Screening (Day 35 to -1)	Baseline (Day 0)	WK2	Wk4	Wk8	Wk12/16	Wk 4	Wk 12		
	Informed Consent w/ Med Hist inc HIV status	x								
Complete PE inc. Vital Signs	x	x								
Symptom Directed PE inc. Vital Signs			x	X	X	X	x	x		
12-lead ECG	x									
Chemistry(Comprehensive Metabolic Panel)	x	x	x	x	x	x	x	x		
Hematology	x	x	x	x	x	x	x	x		
Virology(HCV)	x	x	x	x	x	x	x	x		
AEs		X	X	X	X	X	X	X		
Con Meds	X	X	X	X	X	X	X			
MEMS download		x	x	x	x	x				

Data Collection

At each visit, the following data are to be collected: HCV RNA PCR viral load, CBC, complete metabolic profile, number of pills missed. For both groups, Number of times pill bottles were opened will also be collected.

Primary outcome measures:

Primary endpoint in the study is the effect of the use of Portal724-MEMS Service on medication adherence, defined as compliance to regimen $\geq 95\%$ of the time.

Secondary outcome measures:

The secondary endpoints for the study include the effect of the use of Portal724-MEMS Service on SVR, factors that affect medication adherence, such as race/ethnicity, age, educational attainment. Additionally, the feasibility of using MEMS adherence technology in an inner city urban population will be evaluated.

Statistical Analysis

This is a pilot study intended to generate initial data on the use of MEMS technology in an inner city population to assess its feasibility and impact on treatment outcomes in HCV infected patients. Wilcoxon signed-rank test will be used to compare Groups 1 and 2 in terms of achieving adherence 95%.

SVR between the groups will also be analyzed in the same manner. A descriptive analysis will be done outlining patients' profiles. Fischer's exact test will be used to compare baseline characteristics between Groups 1 and 2. Alpha level for all statistical analysis will be set at 0.05.

Toxicity management

Grazoprevir/elbasvir

The following side effects have been reported when MK-5172 in doses ranging from 25 mg to 800 mg or placebo (a tablet that looks the same as the MK-5172 but has no active ingredient) was given for up to 12 continuous weeks to 389 HCV-infected men and women at the same time as other drugs commonly given to HCV patients (pegylated interferon and ribavirin). These side effects were considered to be related to the treatment.

- Decrease in the blood cells that carry oxygen
- Decrease in blood cells that fight infection
- Stomach pain
- Diarrhea
- Upset stomach
- Dry mouth
- Nausea
- Vomiting
- Weakness
- Chills
- Fatigue

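### Can a smart cap on the study drug bottle score 95% compliance when the regimen includes ribavirin, and over which days?

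*Combined protocol and SAP*

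**What the plan says.** The Objective concerns treatment with "grazopravir/elbasvir with or without Ribavirin, defined as compliance to regimen 95% of the time". Primary outcome measures says: "Primary endpoint in the study is the effect of the use of Portal724-MEMS Service on medication adherence, defined as compliance to regimen", at 95% or above. Under Treatment Arms, three of the six groups take ribavirin, all for 16 weeks: genotype 1a "with baseline NS5A polymorphisms with elbasvir/grazoprevir/ribavirin for 16 weeks", genotype 1a or 1b "PegIFN/RBV/PI-experienced with elbasvir/grazoprevir/ribavirin for 16 weeks", and treatment-experienced genotype 4.

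Under Enrollment, Arm 1 receives elbasvir/grazoprevir "with/or without ribavirin for 12 or 16 weeks 1 tablet daily with MEMS Smart Cap with real-time monitoring"; Arm 2 has the same regimen and a cap without real-time monitoring. For Group 1, "the cap of the study drug bottle will be replaced with the Portal724- MEMS Smart Cap"; Group 2 "will be provided MEMS Smart Cap to record study drug bottle opening". The same section has patients in both groups bring all their anti-HCV bottles to each visit for a pill count. Data Collection lists pills missed and, for both groups, the number of bottle openings. The visit table has a row for the cap download.

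The Introduction, describing earlier HCV treatment, says "Ribavirin has to be taken twice daily, while Interferon is injectable". No ribavirin schedule for this study is given. The DILI and Allergic Reaction sections direct some patients to be withdrawn. Neither Statistical Analysis section defines a numerator or a denominator.

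**The concern.** Read strictly, the endpoint covers everything the patient is prescribed, but the device is described for one bottle. On that reading, in half of the listed groups the cap could call a patient adherent who had missed much of the ribavirin. A pooled pill count could do the reverse, with complete ribavirin intake hiding missed tablets.

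Separately, the plan does not say whether the percentage is taken over prescribed or treated days, or how a day without a cap record is scored. That could affect any of the 40 patients. With 20 per group, one reclassified patient moves a group's rate by 5 percentage points. The trial is open-label and tests at 0.05, so leaving the source and denominator open invites the worry that they will be chosen after the data are seen.

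**Working it through.** **Nothing to reproduce.** The only stated figure is 2 × 20 = 40 patients. No adherence rate, effect size or power accompanies it.

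**Inputs.** Course lengths are 12 weeks (84 days) and 16 weeks (112 days), and the threshold is 95%. Ribavirin at one or two intakes a day is an assumption, because the study's schedule is not stated. Doses needed = 0.95 × scheduled doses, rounded up.

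**Once-daily tablet.**
- 84 days: 0.95 × 84 = 79.8, so 80 needed and 4 may be missed.
- 112 days: 0.95 × 112 = 106.4, so 107 needed and 5 may be missed.

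**Pooled regimen over 16 weeks.**

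| Ribavirin intakes a day (assumed) | Total intakes | Needed | May miss | Cap and regimen disagree from (all tablets taken) |
|---|---|---|---|---|
| 1 | 112 + 112 = 224 | 213 | 11 | 12 of 112 ribavirin missed (10.7%): 212/224 = 94.6% |
| 2 | 112 + 224 = 336 | 320 | 16 | 17 of 224 ribavirin missed (7.6%): 319/336 = 94.9% |

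In reverse, with all ribavirin taken, a pooled count would pass 11 or 16 missed tablets, against 5 for the tablet alone. The plan does not propose a pooled count.

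**Denominator.** Withdrawal after day 42 with no missed dose gives 42/84 = 50%, 42/112 = 37.5%, or 42/42 = 100% of treated days.

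**One patient.** 1/20 = 5 points. For illustration, a two-sided Fisher exact test gives p = 0.044 for 19/20 v 13/20 and p = 0.127 for 18/20 v 13/20. The plan names a different test for adherence, and this fragility belongs to groups of 20 whichever adherence rule is used.

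**How many patients.** Three of six counts listed groups, not patients. If inclusion criterion 2 (treatment naive) is applied, only the genotype 1a group with polymorphisms still yields ribavirin patients. No group sizes are given. If 10%, 25% or 50% of the 40 took ribavirin, that would be 4, 10 or 20 patients.

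**The text side by side.**
- In the Objective, the words about ribavirin describe the treatment received; compliance to the regimen follows as a separate clause.
- The MEMS part of the Introduction says the study uses the elbasvir/grazoprevir combination pill, chosen partly because it is taken once a day. Enrollment puts the cap on the study drug bottle. Together these support scoring the tablet alone, and then endpoint and instrument agree.
- Elsewhere the text uses the plural for bottles and caps. That may only reflect several patients, but the plan is silent on a ribavirin cap, not against one.
- If ribavirin is to count, the pill count on all anti-HCV bottles reaches it.

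**The case for a change.** The strongest case for acting is that no section names the primary source, the denominator or a combining rule, and writing these down costs a few sentences and no patients. The trial tests adherence at 0.05 and may lead to a larger study, so whether a patient reached 95% should be reproducible. The denominator question does not depend on ribavirin at all. Pill counts are only a partial answer, since the Introduction calls that method imprecise when describing earlier studies.

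The gap is real, and that much stands. The stronger claim, that the cap cannot score the endpoint, does not: it needs the whole-regimen reading, a single cap and the cap as sole source, none of which the plan states. The counts of missed ribavirin intakes also rest on a schedule the plan does not give.

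Nor is there one plainly better rule. Prescribed days count protocol-directed withdrawals as non-adherence; treated days ignore early stopping. Scoring every day without a record as missed penalises device failure, although the cap's store-and-forward feature already covers loss of signal. Leaving ribavirin out makes the endpoint clean but narrower; bringing it in needs a second cap or reliance on counts. Each choice is defensible.

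**Conclusion.** No change to the plan follows. This is an endpoint definition left unwritten in a 40-patient pilot, together with a choice among defensible scoring rules. An analyst would most likely score the elbasvir/grazoprevir tablet from the cap and use the pill count for comparison, which is close to what a rewrite would ask for. Caps and pill counts apply in both arms, so the direction of any effect on the arm difference is undetermined.

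The size is conditional. For ribavirin patients, cap and pooled regimen part at 12 missed of 112 or 17 of 224 intakes, under assumed schedules and a pooled score the plan does not propose. For early withdrawal at day 42, the score runs from 37.5% or 50% to 100%. Neither the number on ribavirin nor the number of withdrawals can be derived from the documents. The dosing-frequency wording in the Introduction and in Enrollment must be reconciled by the sponsor; that is a clinical matter, separate from this conclusion.

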This is a pilot study intended to generate initial data on the use of MEMS technology in an inner city population to assess its feasibility and impact on treatment outcomes in HCV infected patients. Wilcoxon signed-rank test will be used to compare Groups 1 and 2 in terms of achieving adherence $\geq 95\%$. SVR between the groups will also be analyzed in the same manner. A descriptive analysis will be done outlining patients' profiles. Fischer's exact test will be used to compare baseline characteristics between Groups 1 and 2.

Scientific Data Dissemination

It is the intention of the study investigators to submit abstracts & present results of this pilot study at major scientific congresses such as AASLD (American Association for Study of Liver Diseases) or DDW (Digestive Disease Week). The final results of study will be submitted for publication in a major peer reviewed medical journal in Infectious Diseases or Gastroenterology as deemed appropriate at the end of study.

Significance of Research Outcomes

The findings of this research study will have significant implications on our understanding of patient adherence to treatment and health care outcomes. If the use of MEMS technology proves feasible & useful in this inner city environment based on this pilot trial, the investigators envision embarking on a larger research initiative to fully use the technology in patients with HCV, HIV and other chronic infectious and non-infectious disease conditions.

References

- [1] European Association for Study of Liver. EASL Clinical Practice Guidelines: management of hepatitis C virus infection. J Hepatol. 2014 Feb;60(2):392-420.
- [3] Centers for Disease Control and Prevention. (2014). Hepatitis C information for health professionals. Retrieved from <http://www.cdc.gov/hepatitis/hcv/>

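### The only planned between-arm comparison of adherence is yes/no at 95%, by a paired test that does not fit two independent arms; no graded comparison of the cap data is prespecified

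*Combined protocol and SAP*

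**What the plan says.** - **Endpoint.** Under Primary outcome measures: "Primary endpoint in the study is the effect of the use of Portal724-MEMS Service on medication adherence, defined as compliance to regimen" at least 95% of the time. The Objective uses the same cut-off.
- **Test.** Both copies of the Statistical Analysis section say: "Wilcoxon signed-rank test will be used to compare Groups 1 and 2 in terms of achieving adherence" of 95%. SVR is to be analysed in the same manner. Fisher's exact test is named only for baseline characteristics. The first copy adds: "Alpha level for all statistical analysis will be set at 0.05".
- **Design.** Under Enrollment: "the patient will be randomized to either ARM 1 or ARM 2 in a 1:1 ratio". Under Methods: "Proposed number of participants: 40 patients infected with HCV (20 for each group").
- **Secondary endpoints.** "The secondary endpoints for the study include the effect of the use of Portal724-MEMS Service on SVR, factors that affect medication adherence". Demographic characteristics are given as examples of these factors, and feasibility is also listed. None compares a graded adherence measure between arms. The scale of adherence in the factor analysis is not stated.
- **Data.** The MEMS section says that the cap logs each dispensing event with date and time. Data Collection has bottle openings recorded for both groups and missed pills at each visit. The schedule of procedures has a cap download from baseline to week 12/16. Dosing is one tablet daily for 12 or 16 weeks.

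**The concern.** The cap gives a dated record for each patient, and the planned comparison reduces it to one yes/no. A patient just under 95% then counts the same as one who took fewer than half the doses. With 20 patients per arm, a binary comparison is imprecise.

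The stated purpose is to generate initial data, and the investigators envisage a larger study if the technology proves useful. Planning that study calls for the spread of adherence and an effect estimate with an interval. Two proportions from 20 patients each supply only part of this. If no graded measure is fixed beforehand, any that is reported later will have been chosen after the data were seen.

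The test adds a second problem. A signed-rank test works on within-pair differences. The arms are randomized in parallel and nothing in the documents pairs patients across them, so the primary comparison cannot be carried out as named.

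**Working it through.** **Inputs from the documents.** 20 per arm, 1:1, alpha 0.05, once-daily dosing for 12 or 16 weeks, cut-off 95%. The plan gives no power, control rate, effect size or spread of adherence, so it has no figure to reproduce. Two-sided testing and every adherence distribution below are assumptions.

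**1. What the cut-off does to the record.**
- 12 weeks: 12 × 7 = 84 doses; 0.95 × 84 = 79.8, so 80 or more passes (up to 4 missed).
- 16 weeks: 16 × 7 = 112 doses; 0.95 × 112 = 106.4, so 107 or more passes (up to 5 missed).
- A patient with 79/84 = 94% and one with 34/84 = 40% both count as failures.

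**2. Power of a binary comparison, 20 per arm.** Power is the sum over all outcome pairs (a, b) of Bin(a; 20, p0) × Bin(b; 20, p1), taken where the test gives p ≤ 0.05.

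| Reaching 95%: control vs feedback | Fisher exact | Uncorrected chi-square |
|---|---|---|
| 50% vs 75% | 27% | 37% |
| 50% vs 80% | 41% | 53% |
| 60% vs 80% | 19% | 29% |
| 60% vs 90% | 49% | 62% |

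With equal proportions of 30%, 50% or 70%, the actual size is 0.020 to 0.025 for Fisher and 0.043 to 0.053 for chi-square. Part of any gain over Fisher therefore reflects Fisher's conservatism and not information lost at the cut-off.

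**3. Graded against binary under an assumed mean shift.** Each patient's adherence is drawn from Beta(m·s, (1−m)·s), where m is the arm mean and a larger s means less spread between patients. Doses taken are Bin(84, p), and 80 or more passes. There were 6,000 simulated trials per scenario, with the rank-sum test applied to percent adherence.

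| Means, s | Rank-sum | Fisher | Chi-square | Gain over Fisher / chi-square (points) |
|---|---|---|---|---|
| 88% vs 95%, 10 | 81% | 52% | 64% | 29 / 17 |
| 88% vs 95%, 20 | 93% | 72% | 81% | 21 / 12 |
| 90% vs 95%, 10 | 59% | 30% | 41% | 29 / 18 |
| 93% vs 97%, 10 | 61% | 30% | 42% | 31 / 19 |
| 85% vs 95%, 20 | 99% | 93% | 96% | 6 / 3 |
| 80% vs 90%, 20 | 95% | 53% | 67% | 42 / 28 |

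Over all 24 scenarios (control means 80% to 93%, active means 90% to 98%, s = 5, 10 or 20), the gain was 6 to 42 points over Fisher and 3 to 28 over chi-square. In 18 of the 24 it was 21 to 32 over Fisher and 12 to 19 over chi-square.

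**4. An effect only across the threshold.** Here adherence is uniform over 60–94% for those below the cut-off and over 95–100% for those above it. The effect only moves patients from the lower group to the upper.

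| Reaching 95% | Rank-sum | Fisher | Chi-square | Difference from Fisher / chi-square (points) |
|---|---|---|---|---|
| 50% vs 75% | 27% | 27% | 37% | 0 / −10 |
| 50% vs 80% | 36% | 41% | 53% | −5 / −17 |
| 60% vs 90% | 38% | 49% | 62% | −12 / −25 |

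The sign of the difference thus depends on how the intervention works, which the documents do not settle.

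**The case against.** The strongest reply is that this is a pilot for feasibility with no power claim, so an absent secondary endpoint is an option not taken and contradicts no stated figure. That stands as far as it goes: no number in the plan is wrong. Two arm proportions also carry some planning information, and the patient-level data remain available. But a pilot without a power claim depends all the more on estimation, and a measure fixed in advance is worth more than one chosen afterwards.

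Four stronger readings are tempting and are not supported.

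- **A reader might infer that the cap data are discarded.** They are downloaded and collected in both arms, and the factor analysis may use them on a scale the plan does not state. What is missing is a prespecified graded comparison between arms.
- **A reader might infer a fixed loss of 20 to 30 points of power.** That size appears mainly against Fisher's test, which the plan does not name for this endpoint, and under assumed mean shifts. Against chi-square it is smaller, and it can reverse. Feedback that consists of a call after a missed dosing time need not produce a smooth shift in the mean.
- **A reader might infer that the added analysis restores power to the primary.** It answers a different question with its own power. The primary, as named, has no defined power to restore.
- **A reader might infer that a Wilcoxon test cannot be used on a yes/no outcome.** A rank-sum test can be run on 0/1 data with ties; for 50% vs 80% its power is 49%. The error is the paired version on independent arms.

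It is also fair to object that a graded measure needs definitions the plan lacks: whether compliance comes from cap openings or pill counts, and how days after early discontinuation count. Withdrawal is foreseen in the DILI and Allergic Reaction sections. The binary primary has the same gaps.

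**Conclusion.** The point holds as a gap in the analysis plan. Two parts rest on the text alone: adherence is compared between arms only at the 95% cut-off although graded records exist in both arms, and the named test is for paired data.

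The size rests on assumptions. Under beta-binomial mean shifts with 20 per arm, the graded test often has roughly 10 to 30 points more power than a binary test. That is about 11 to 20 over chi-square and more over Fisher, partly because Fisher's actual size is about half the nominal level. If feedback acts only across the threshold, there is no gain or a loss of up to 12 points against Fisher and 25 against chi-square in the cases tried. This is why the graded analysis should sit beside the 95% rule and not replace it. Its main value is a separate, usually more precise effect estimate for the larger study.

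**What to change.** 1. Keep the 95% rule as the primary endpoint. In both copies of the Statistical Analysis section, replace the signed-rank test with a named independent-samples test for a binary outcome, and do the same for SVR. State whether tests are two-sided.
2. Add as first secondary endpoint the percent of prescribed days with a recorded cap opening. Compare the arms by the two-sample Wilcoxon rank-sum test, reported with the Hodges-Lehmann difference and its 95% CI.
3. Before data are examined, fix cap openings as the data source, the denominator for 12- and 16-week courses, and how days after early discontinuation are counted.

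**Cost.** No new patients, visits or data. The cost is one more secondary analysis and the definitions in step 3, which the primary endpoint also needs.

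### The pilot is meant to supply initial data for a possible larger study, but its primary adherence analysis is a significance test alone, with no planned between-arm estimate or confidence interval

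*Combined protocol and SAP*

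**What the plan says.** **Purpose.** The Statistical Analysis section appears twice in the combined document, and both versions open with "This is a pilot study intended to generate initial data on the use of MEMS technology in an inner city population". Under Significance of Research Outcomes, the condition for going on is that the technology proves feasible and useful, in which case "the investigators envision embarking on a larger research initiative to fully use the technology". Neither word is given a criterion.

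**Design.** Methods gives "Proposed number of participants: 40 patients infected with HCV (20 for each group"), and Enrollment states that "the patient will be randomized to either ARM 1 or ARM 2 in a 1:1 ratio". No power, effect size, control rate, precision target or dropout allowance accompanies the number.

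**Primary endpoint.** Primary outcome measures names the "effect of the use of Portal724-MEMS Service on medication adherence, defined as compliance to regimen" at least 95% of the time.

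**Planned analysis.** "Wilcoxon signed-rank test will be used to compare Groups 1 and 2 in terms of achieving adherence 95"%. The first Statistical Analysis section adds: "Alpha level for all statistical analysis will be set at 0.05". The second omits the alpha level. SVR is to be handled in the same way. Descriptive analysis is confined to patient profiles. Feasibility is listed among the secondary outcomes without a measure.

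**The concern.** The primary endpoint is worded as an effect, yet the plan never says that the effect will be estimated. To plan a larger trial, the investigators would need three things from this pilot: the control-arm rate, the difference between arms, and the uncertainty of each. None of these is a planned result. What is planned is a test outcome, and at 20 per arm that says little unless the effect is very large.

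The risk is in interpretation. A substantial observed gain could come out non-significant and, with no estimate or interval required beside it, be read as no effect. The point concerns the form of the primary result. It would remain if the paired test named in the plan were replaced by a suitable unpaired one, and it is not a complaint about the number of patients.

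**Working it through.** **Inputs from the documents:** 20 per arm, 1:1 allocation, alpha 0.05, a yes/no outcome at the 95% threshold.

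**Assumptions, because the documents are silent:** two-sided testing, no dropout, control-arm share reaching the threshold between 30% and 70%, and a 25-point gain as the illustrative effect. The plan states no power, so there is no figure of its own to reproduce.

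**Step 1: chance of missing a 25-point gain.** Let x be the number adherent in Arm 1 and y the number in Arm 2. Power is the sum, over all 21 x 21 pairs (x, y) with p at or below 0.05, of Bin(x; 20, p1) x Bin(y; 20, p2). The miss rate is 1 minus power.

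| Control v intervention | Fisher's exact: power (miss) | Chi-square, uncorrected: power (miss) |
|---|---|---|
| 30% v 55% | 24.5% (75.5%) | 34.6% (65.4%) |
| 40% v 65% | 23.0% (77.0%) | 33.0% (67.0%) |
| 50% v 75% | 26.9% (73.1%) | 37.5% (62.5%) |
| 60% v 85% | 31.7% (68.3%) | 44.1% (55.9%) |
| 70% v 95% | 44.6% (55.4%) | 59.1% (40.9%) |

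The miss rate therefore runs from about 41% to 77%. Two other tests stay within that range. A rank-sum test on the yes/no outcome has power of about 32% to 59%. The signed-rank test as literally named, applied to arbitrary pairs at control rates of 40% to 70%, has power of 23% to 34% (exact) or 31% to 55% (asymptotic). The plan does not state sidedness. One-sided at 0.05, the normal approximation gives power of about 48% to 68%, a miss rate of about 32% to 52%.

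**Step 2: what a test and an estimate each report for the same data.** Take 15/20 in Arm 1 and 10/20 in Arm 2.

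- Chi-square: pooled proportion 25/40 = 0.625; z = 0.25 / sqrt(0.625 x 0.375 x 2/20) = 0.25 / 0.1531 = 1.63; p = 0.10.
- Fisher's exact: p = 0.19.
- Wilson 95% limits: 0.531 to 0.888 for 15/20; 0.299 to 0.701 for 10/20.
- Newcombe lower limit: 0.25 - sqrt((0.75 - 0.531)² + (0.701 - 0.50)²) = 0.25 - 0.297 = -0.047.
- Newcombe upper limit: 0.25 + sqrt((0.888 - 0.75)² + (0.50 - 0.299)²) = 0.25 + 0.244 = 0.494.

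The test alone says not significant. The estimate says +25 points, 95% interval -5 to +49, with a control rate of 50% (30% to 70%). For 17/20 v 12/20, p is 0.08 (chi-square) or 0.16 (Fisher) and the interval is -3 to +48.

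**Step 3: precision on offer.** The Wald half-width is 1.96 x sqrt(p1(1 - p1)/20 + p2(1 - p2)/20). At 50% v 75% this is 1.96 x sqrt(0.0125 + 0.009375) = 0.290. At 60% v 85% it is 0.266, and at 70% v 95% it is 0.222. So the interval is about +/-22 to +/-29 points wide on each side. The Newcombe interval for 15/20 v 10/20 is similar: (0.494 + 0.047)/2 = 0.27.

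**The case against.** **Low power is normal in a pilot, and an interval does not cure it.** This stands. Checked by the same enumeration, the Newcombe interval at 20 per arm would exclude zero only about 37% of the time at 50% v 75% and 44% at 60% v 85%, much as chi-square does. The gain from an interval is in what is reported, not in power.

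**The estimates come free with the data.** Bottle openings are collected in both groups and each patient is classified, so the proportions and the difference can be computed whatever the plan says. This also stands: nothing is irrecoverably lost. But nothing commits the investigators to report these figures, and the descriptive analysis that is promised covers patient profiles only.

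**The plan does not make p < 0.05 the rule for proceeding.** A reader might infer that significance is the yardstick for useful, and that the larger study would be dropped without it. The documents do not say so. The alpha sentence covers every analysis, including baseline comparisons, and the condition for a larger initiative is tied to no number. What can be said is that useful is undefined and that no estimate is planned to inform the judgement.

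**The size depends on unstated inputs.** A reader might infer a miss rate of about three in four. That needs Fisher's exact test, which the plan names only for baseline characteristics, and a control rate of about 30% to 50%, which the plan does not give. Higher control rates are plausible: the introduction says adherence has improved with once-daily agents, and both arms are counselled at every visit. At 70% v 95%, chi-square misses about 41%.

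**Conclusion.** The point holds in this form: a pilot intended to generate initial data for a possible larger study has a significance test as the only analysis of its primary endpoint, with no between-arm estimate, no confidence interval and no definition of useful.

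On two-sided testing with no dropout, a true 25-point gain would be missed roughly 40% to 77% of the time. The range reflects the choice between chi-square and Fisher's exact and an assumed control rate of 30% to 70%. Both the control rate and the 25-point effect are assumptions.

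Two further readings are not supported. The sample size is not shown to be wrong, since the plan makes no power claim. Nor does an interval of -5 to +49 exclude meaningful harm, because the documents set no margin for harm. It shows only a lower limit near -5 points with a large benefit still open.

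**What to change.** Amend both copies of the Statistical Analysis section to state that:

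1. The primary result is the proportion of patients at or above 95% adherence in each arm, and the difference (Arm 1 minus Arm 2) with a 95% Newcombe interval.
2. Any p-value comes from a test for two independent groups and is supportive. A value above 0.05 will not be reported as no effect.
3. The larger study will be planned from the estimate and its interval, including the Arm 2 proportion with its own interval, together with the feasibility findings.

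This takes a few sentences and adds no patients, visits or procedures. The downside is that the conclusion will be a wide interval, about +/-22 to +/-29 points, in place of a yes/no statement. The control rate will be equally imprecise (30% to 70% if 10/20 is observed), so planning should use the range and not the point value alone.
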